**F. Data Analysis Plan:** Hospital Roosevelt has 800 pediatric blood cultures processed monthly (with about 5% positivity). Based on preliminary data, only 37% of patients with positive blood cultures received optimal therapy based on predefined consensus guidelines. Of those who receive optimal therapy, the median time to therapy is 90 hours. With the addition of a blood culture identification panel, we expect to see a reduction in time to optimal antimicrobial therapy to 30 hours. This estimate is based on U.S. data conducted at our institution showing a reduction to 27 hours on average with BCID plus antimicrobial stewardship.

Target Enrollment: 100 patients over 4 month study period

**G. Summarize Knowledge to be Gained:** This study is important to evaluate the impact that rapid multiplex blood culture identification PCR panels have on improving clinical outcomes in low-middle income countries such as Guatemala. It has shown significant impact in reduction in time to optimal antimicrobial therapy in high-income countries. In countries such as Guatemala, with higher rates of antimicrobial resistance and broad-spectrum antimicrobial usage, the potential impact is greater and could lead to a mortality benefit. If a significant clinical impact is observed, we would advocate for continued use of the panel at Hospital Roosevelt, as well as 24/7 implementation if a significant difference is seen between the intervention and prospective control group. This could be translatable to other low-middle income countries.

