On-panel true pathogens= Pathogens on the BCID2 panel that are always considered real pathogens per protocol. These include, *E. faecalis*, *E. faecium*, *Listeria*, *Staph aureus*, *Strep pneumonia*, *Strep agalactiae*, *Strep pyogenes*, *Acinetobacter baumannii*, *B. fragilis*, *Enterobacterales*, *Enterobacter cloacae*, *E. coli*, *Klebsiella aerogenes*, *Klebsiella oxytoca*, *Klebsiella pneumoniae*, *Proteus*, *Salmonella*, *Serratia matcescens*, *Haemophilus influenza*, *Neisseria meningitidis*, *Pseudomonas aeruginosa*, *Stenotrophomonas maltophilia*, *Cryptococcus*, *Candida species*.

Gram negative on-panel pathogen= On-panel true pathogens as above that are Gram negatives only. These include *Acinetobacter baumannii*, *B. fragilis*, *Enterobacterales*, *Enterobacter cloacae*, *E. coli*, *Klebsiella aerogenes*, *Klebsiella oxytoca*, *Klebsiella pneumoniae*, *Proteus*, *Salmonella*, *Serratia matcescens*, *Haemophilus influenza*, *Neisseria meningitidis*, *Pseudomonas aeruginosa*, *Stenotrophomonas maltophilia*.

Gram negative pathogen= On or off-panel pathogens that are Gram negatives.

On-panel classic contaminant= Gram positive pathogens on the BCID2 panel that are often considered contaminants (note, may be considered real in the analysis). These include, *Staph epi*, *Staph lugdunensis*, *other Staph species*, *other Strep species*.

Off-panel non-Gram negatives (other)= typically contaminants.

True pathogens (on and off panel)= excluding common contaminants.

Polymicrobial= More than one organism was detected by BCID2 and/or Vitek.

Primary outcomes

Optimal antibiotic=typically narrowest spectrum agent based on predefined consensus guidelines

Effective antibiotic= any antibiotic susceptible based on susceptibilities even if overly broad.

Time to optimal antimicrobial therapy=time blood culture received in lab to time of first dose of “optimal” antibiotic. Censor at 14 days. Censor for death if “never reached” optimal. Stoppage of antibiotics if deemed a contaminant.

Time to effective antimicrobial therapy= time of blood culture received in lab to time of first dose of “effective” antibiotic. Censor at 14 days. Censor for death if “never reached” effective. Stoppage of antibiotics if deemed a contaminant.

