Clinician discretion (Intention to treat analysis (ITT))=effective and optimal therapy determined based on whether **treating physicians** considered the pathogen real or a contaminant. Optimal therapy allowed additional antibiotics if the treating team was also treating for other syndromic diagnoses, such as culture-negative sepsis (if pathogen detected deemed to be a contaminant), nosocomial pneumonia, etc. if called out in diagnoses. Definitions created for optimal therapy for nosocomial pneumonia, culture-negative sepsis, etc.

- Time to effective therapy in ITT:
 - Time from blood culture received in lab (time 0) to effective therapy
 - Time from blood culture positivity (time 0) to effective therapy
- Time to optimal therapy in ITT:
 - Time from blood culture received in lab (time 0) to effective therapy
 - Time from blood culture positivity (time 0) to effective therapy

Pathogen directed (Per protocol analysis) =effective and optimal therapy based on **strict definitions** for real pathogen or contaminant created by study team. Strict optimal antibiotic definitions without allowing for additional antibiotics for culture-negative sepsis or nosocomial pneumonia, etc. Does allow for additional antibiotics for clear other indications (pyelonephritis, CAP, dacrocystitis, intra-abdominal abscess, etc.) or another organism isolated (excluding urine and trach cultures). Not allowing for more controversial diagnoses such as sepsis or nosocomial pneumonia.

- Time to effective therapy in per protocol:
 - Time from blood culture received in lab (time 0) to effective therapy
 - Time from blood culture positivity (time 0) to effective therapy
- Time to optimal therapy in per protocol:
 - Time from blood culture received in lab (time 0) to effective therapy
 - Time from blood culture positivity (time 0) to effective therapy

Secondary outcomes

Time to pathogen identification= Time from time of blood culture receipt in lab (time 0) to identification of a pathogen. For control patients, this is the time to Vitek. For intervention patients, this is the time to BCID2 if the BCID2 was positive for an on-panel pathogen or time to vitek if the BCID2 was negative.

- Control: time to Vitek
- Intervention:
 - If BCID2 positive → calculate time to BCID2 result
 - If BCID2 negative → calculate time to Vitek

Total antibiotic days=all days that patient was on antibiotics (any dose of antibiotic) from date that blood culture was drawn. Capped at 14 days or date of death.

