Antibiotic days of therapy =Sum of antibiotics each day over 14-day period. For example if 2 antibiotics were each given over 5 days, this would count as 10 DOT.

Number of different antibiotics=Number of unique antibiotics given over the 14-day period.

Length of stay=date admitted to date patient left the study (date of death/discharge or lapse of 30 days). Censor at 30 days.

Total ICU days=date admitted in ICU to date transferred out or date of death/discharge. Censor at 30 days.

Time to death= Time from blood culture obtained to time of death.

Number of deaths within 24h of blood culture draw= Use time of death calculation above to determine the number of patients who died <24h

Overview of Analyses to perform:

- All interventions vs. all concurrent controls (including protocol deviations) vs. historical controls
 - Demographics
 - All outcomes (primary and all secondary endpoints)
 - Sensitivity analysis comparing weekday vs. weekend controls
- Per protocol controls vs. per protocol intervention (excluding protocol deviations)
 - Demographics
 - All outcomes (primary and all secondary endpoints)
- Clinician discretion (ITT) analysis (controls vs. interventions)

- Number of contaminants vs. true pathogens
- Time to optimal therapy
- Time to effective therapy
- Pathogen directed (Per protocol) analysis (controls vs. interventions)
 - Number of contaminants vs. true pathogens
 - Time to optimal therapy
 - Time to effective therapy
- Gram negatives only (on- and off- panel)
 - Demographics
 - Time to optimal therapy
 - Time to effective therapy
 - Mortality
- On-panel true pathogens only
 - Demographics
 - Time to optimal therapy
 - Time to effective therapy
 - Mortality
- On-panel Gram negatives only
 - Demographics
 - Time to optimal therapy
 - Time to effective therapy
 - Mortality
- True pathogens (on and off panel)
 - Demographics
 - Time to optimal therapy
 - Time to effective therapy
 - Mortality

Figure 1: CONSORT Diagram

Table 1: Patient Characteristics

*Wilcoxon test of medians

**chi-square test

Table 1A: Supplemental table with demographics from sub-groups.

	Per protocol Intervention	Per protocol Control	p-value	True on-panel pathogen Intervention	True on-panel Pathogen controls	p-value	All Gram negative (GN) Interv.	All GN control	p-value	All GN weekDAY controls	p-value (compare to GN interv.)	On-panel GN Interv.	On-panel GN control	p-value

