Table 3B: For non-NICU patients only

Table 3C: Table of outcomes with sub-groups for all units

	Per protocol interventions	Per protocol Controls	p-value	All Gram negative interventions	All Gram negative controls	p-value	All GN weekDAY controls	p-value (compare to GN interv.)	True on-panel pathogens interventions	True on-panel pathogens controls	p-value	On-panel Gram neg interv	On-panel Gram neg control	p-value
--	----------------------------	-----------------------	---------	---------------------------------	----------------------------	---------	-------------------------	---------------------------------	---------------------------------------	----------------------------------	---------	--------------------------	---------------------------	---------

Median total antibiotic days (XX days)													
Median antibiotics DOT													
Number of unique antibiotics in 14-day period													

Table 4: BCID2/Vitek discrepancies in intervention patients

	Number of patients (N, %)
BCID2/Vitek agreed	
BCID2/Vitek disagreed	
BCID2 positive, Vitek negative	
BCID2 negative, Vitek positive	
Species misidentification	
Resistance gene did not match susceptibility	
Organism not on panel	

Other parameters:

- Look at distribution (median with IQR) of time between BCID2 result and team notification (only for intervention patients).
- Look at distribution (median with IQR) of time between BCID2 execution and team notification (only for intervention patients).
- Age distribution and gender between those excluded via initial screening and those included (initially enrolled).

Figures: Kaplan Meier curves for time to optimal and time to effective therapy (using both intention to treat AND per protocol analyses)

1st way- time of blood culture draw as time 0

2nd way- time of blood culture positivity as time 0

Figure 1: Compare interventions vs. concurrent controls vs. Historical controls (all pathogens)

Figure 1A: time to effective therapy ITT

Figure 1B: time to effective therapy per protocol

Figure 1C: time to optimal therapy ITT

Figure 1D: time to optimal therapy per protocol

Figure 1E: time to death (deaths only)

Figure 2: Compare interventions vs. concurrent controls vs. Historical controls (Gram negative rods on-panel and off-panel)

Figure 3: Compare interventions vs. concurrent controls vs. Historical controls (True on-panel pathogens only)

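### Censoring deaths before therapy makes the Kaplan-Meier curves modestly overstate the share of children who reach therapy; the deaths-only Figure 1E can describe timing of death but not mortality

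*SAP*

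**What the plan says.** In the SAP definitions under Primary outcomes, time to optimal therapy carries the rule "Censor at 14 days. Censor for death if “never reached” optimal". Time to effective therapy has the matching rule "Censor for death if “never reached” effective". The Figures list then calls for "Kaplan Meier curves for time to optimal and time to effective therapy" in the intervention, concurrent control and historical control groups. Neither document mentions competing risks, cumulative incidence or a sensitivity analysis for death.

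The rule does not say at what time a child who dies is censored. The plain reading is the time of death. The SAP uses that stop for a neighbouring variable, total antibiotic days: "Capped at 14 days or date of death".

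The same list includes "Figure 1E: time to death (deaths only". Time to death is defined from the time the culture was obtained, with no censoring time for survivors. Mortality is also a secondary outcome in its own right and is compared between groups in the overall, per-protocol and subgroup analyses.

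**The concern.** Death rules out later therapy. Censoring at death treats the child as someone who might still have been treated and passes that child's weight to those still at risk. One minus Kaplan-Meier therefore exceeds the true share whenever a death before therapy precedes a later therapy event. The direction is awkward: a group with more such deaths looks better at reaching therapy.

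This is the primary endpoint. Historical mortality was 20% (Protocol section III). The SAP plans to report "Number of deaths within 24h of blood culture draw", while historical pathogen identification took 34 to 122 h, so some deaths before culture-directed therapy are plausible. The Protocol summarises its historical cohort by a crude share at optimal therapy, 37%. A Kaplan-Meier curve with deaths censored is not on that scale.

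Figure 1E raises a separate and smaller matter. If it is restricted to children who died, every group's curve falls to zero whatever its mortality.

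**Working it through.** The documents contain no calculation on this point to reproduce, so the check compares the two estimators under stated assumptions.

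**Inputs from the documents.** Historical cohort of 99; 37% reached optimal therapy, median 90 h among them; mortality 20% (Protocol section III). Expected effect: "we expect to see a reduction in time to optimal antimicrobial therapy to 30 hours" (Protocol section IV.F). Group sizes 135, 219 and 99 (SAP Table 2). Horizon 14 days = 336 h.

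**Assumptions.** Therapy and death times are truncated exponential on 0 to 336 h. Median time to death is 24, 48, 96 or 160 h. The share dying before therapy is 5%, 10% or 20%. The documents give neither the timing of deaths nor therapy status at death.

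**Formula.** Let F1(t) be the true cumulative share treated and F2(t) the share dead before therapy. Then 1 − KM(t) = 1 − ∏[1 − dF1/(1 − F1 − F2)], while the cumulative incidence is F1(t).

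**Bound by hand.** Take 99 children, 37 treated and 20 deaths, all before the first therapy event. Then 1 − KM = 1 − 42/79 = 37/79 = 46.8%, against a true 37/99 = 37.4%. If all 20 deaths follow the last therapy event, the curve reads 37.4%.

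**Optimal therapy, true share 37%, median 90 h: one minus Kaplan-Meier at 14 days (%).**

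| Die before therapy | Death median 24 h | 48 h | 96 h | 160 h |
|---|---|---|---|---|
| 5% | 38.65 | 38.41 | 38.08 | 37.80 |
| 10% | 40.49 | 39.96 | 39.27 | 38.66 |
| 20% | 44.85 | 43.64 | 42.02 | 40.65 |

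In a group of 219 the true count is 0.37 × 219 = 81. The 20% row would read as 0.4065 × 219 = 89 to 0.4485 × 219 = 98.

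**Unequal deaths, equal true share.** With 20% against 10% dying first, the false gap at 14 days is 2.0 to 4.4 points. With 10% against 5% it is 0.9 to 1.8 points. At 72 h (true share 15.6%) the 20% against 10% gap is 0.2 to 1.1 points.

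**Equal deaths, different speed.** Both arms truly reach 37%, with medians of 30 h and 90 h, and 20% die first in each. At 14 days the 30 h arm reads 42.74, 40.98, 39.39 and 38.38, so the slower arm reads 2.1 to 2.7 points higher although the shares are equal. With 10% deaths this is about 1 point. At 72 h the true difference is 30.0 − 15.6 = 14.4 points, and with 20% deaths the curves show 14.6 to 15.9.

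**Yardstick.** The standard error of a difference in proportions at 37% is √[0.37 × 0.63 × (1/135 + 1/219)] = 5.3 points, and √[0.37 × 0.63 × (1/135 + 1/99)] = 6.4 points against historical controls. All the false gaps above are smaller. A 15-point difference in deaths with the earliest timing would give 44.85 − 38.65 = 6.2 points, but that needs every historical-level death to come first in one group only.

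**Effective therapy.** The documents give no share. If 60% to 80% truly reach it (median 24 to 48 h) and 5% die first, the overstatement at 14 days is 0.5 to 3.8 points.

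**Figure 1E.** At 20% mortality it would use 0.20 × 135 = 27 and 0.20 × 219 ≈ 44 children. Each curve runs from 100% to 0%, so groups with different mortality but the same timing of death have the same expected curve.

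**The case against.** - **The primary outcome is a time, and comparing times is sound.** This stands. A log-rank or Cox comparison with deaths censored is valid for the cause-specific hazard, that is, for speed of therapy among children alive and untreated. A reader might infer that the primary comparison is biased; the documents do not support that. Nor would a median change in the 37% scenarios: the curve stays below 50% (bound 46.8%), so the median is not reached under either estimator.
- **The 20% scenario is a ceiling.** This stands. It is total historical mortality, with no time window or therapy status. Children also start empirical antibiotics, so death before identification is not the same as death before therapy.
- **The share treated may already be tabulated.** This stands. The rows of the outcome tables are largely unreadable in the extracted text, so no claim is made that a crude share is missing.
- **Deaths might be kept at risk to day 14.** The curve would then equal the cumulative incidence, absent other censoring. The SAP does not say this, and its wording on antibiotic days points the other way, though for a different variable. The ambiguity is itself a reason to state the time.
- **Figure 1E may be only descriptive.** This is fair. The SAP assigns it no comparative purpose, and its wording might loosely mean death as the only event. A reader might infer that the trial lacks a mortality comparison; it does not, because mortality is compared elsewhere.

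**Conclusion.** The point holds as a modest, systematic overstatement in the plotted share reaching therapy, and it should be fixed. With 37% truly treated, the 14-day reading is about 38% to 40% if 5% to 10% die first and about 41% to 45% at the 20% upper limit. False gaps between groups stay below one standard error for differences of up to 10 points in deaths before therapy. The distortion is smallest early, where most of the expected effect lies, but a larger sample would not remove it. These sizes rest on assumed timing and on censoring at the time of death. If no death before therapy precedes a later therapy event, the bias is zero. Figure 1E is a minor labelling point.

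**What to change.** 1. Draw the time-to-therapy figures as Aalen-Johansen cumulative incidence to 14 days, with death before therapy as a competing event. Read the share at therapy, for example at 72 h and 14 days, from these curves.
2. Keep the cause-specific comparison for speed. In the definitions of both therapy endpoints, state that deaths are censored at the time of death for that comparison, and say how live discharge before therapy is handled.
3. Label Figure 1E as a description of when deaths occur. Alternatively, replace it with the cumulative incidence of in-hospital death in all patients from the time the culture was obtained, with live discharge as a competing event and a horizon stated from culture. The SAP's existing limit, "date patient left the study (date of death/discharge or lapse of 30 days", belongs to length of stay, which starts at admission. Cultures may turn positive during a stay, so that limit cannot simply be carried over.

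The cost is SAP wording and a little more analysis in standard software, using death and discharge dates the SAP already relies on. The plotted share reaching therapy becomes slightly lower, and a redrawn Figure 1E would cover in-hospital death only.

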Rapid Blood Culture Identification Panel in Pediatric Patients in Guatemala

NCT05314816

Statistical Analysis Plan

v. 2/23/2023

Statistical Analysis Plan

Objective: to evaluate the clinical impact of the BioFire BCID2 panel in children with bacteremia in Guatemala.

Study Design: Pragmatic clinical trial comparing intervention to two different control groups. Intervention and concurrent control group allocated by time of blood culture positivity. Also comparing to historical controls.

Primary outcome: time to optimal antimicrobial therapy

Secondary outcomes:

- Time to effective antimicrobial therapy
- Time to pathogen identification
- Mortality
- Length of hospital stay
- Antibiotic days of therapy (DOT)
- Number of unique antibiotics
- Total ICU days

Definitions to consider:

Patient Group

Intervention= patient was enrolled in the intervention group and received the BCID2 intervention within 12h timeframe

Concurrent control= patient was enrolled in the study and did not receive the BCID2 intervention within 12h from blood culture positivity

- Weekday controls= Patient with positive blood culture from 1pm-11:59pm Mon-Thurs
- Weekend controls= Patient with positive blood culture from 1pm Fri- 11:59pm Sunday

Per protocol =patient received intervention based on original allocation.

- Per protocol intervention= Patient allocated to intervention based on timing of blood culture AND BCID2 was performed within 8h timeframe.
- Per protocol control= Patient allocated to control group based on timing of blood culture AND no BCID2 was performed.

Protocol deviation=Patient intended to remain in the allocated group, but there was an unintentional deviation from protocol.

- Protocol deviation intervention= BCID2 run between 8-12h in patient allocated to intervention.
- Protocol deviation control= BCID2 was sent clinically >12h from positive culture in patient allocated to control group OR patient originally allocated to intervention group but BCID2 was not performed.

Sub-groups

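### The SAP's four set-specific definition lines for time to optimal therapy end at effective therapy, and no listed Kaplan-Meier curve for optimal or effective therapy starts at lab receipt

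*SAP*

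**What the plan says.** The SAP opens with "Primary outcome: time to optimal antimicrobial therapy". Protocol section IV.A starts that outcome at receipt of the specimen in the laboratory, and starts time to effective therapy there too. The SAP's Primary outcomes section agrees. It ends the optimal outcome at the first optimal dose, adds 14-day and death censoring and a contaminant rule, and defines effective therapy as a separate event.

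The SAP then defines two analysis sets, each with its own meaning of optimal. Under clinician discretion (labelled ITT), "Optimal therapy allowed additional antibiotics if the treating team was also treating for other syndromic diagnoses". Under the pathogen-directed set (labelled per protocol), the rule is "Strict optimal antibiotic definitions without allowing for additional antibiotics for culture-negative sepsis or nosocomial pneumonia, etc".

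Each set lists its time intervals. Under both "Time to optimal therapy in ITT" and "Time to optimal therapy in per protocol" the two lines are "Time from blood culture received in lab (time 0) to effective therapy" and "Time from blood culture positivity (time 0) to effective therapy".

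The Figures section plans Kaplan-Meier curves for optimal and effective therapy in both sets, in two ways: with culture draw as time zero, and with positivity as time zero. Panels 1A and 1B are for effective therapy, 1C and 1D for optimal therapy, and 1E for time to death.

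**The concern.** There are two separate faults.

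The first is the event. Effective therapy is any active agent, however broad, while optimal therapy is typically the narrowest agent under the consensus guidelines. A patient can reach the first without the second. The set-specific lines are what a programmer would code from, and under the optimal headings they name the secondary outcome's event. For lab receipt, the Primary outcomes section supplies the right event. For positivity, no other definition line exists.

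The second is the time zero of the figures. Both therapy outcomes start at lab receipt in the protocol and in the SAP definitions, but receipt is not among the time zeros listed for the curves. If draw means draw, each plotted time is longer than the defined one by that patient's draw-to-receipt interval. If that interval differs between groups, historical controls included, the visual comparison changes as well as the axis. At stake is whether the main display of the primary outcome matches its definition.

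**Working it through.** No formula applies. The check is a count and a comparison of wording.

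**Event.** The set-specific definitions contain 2 outcomes × 2 analysis sets × 2 time zeros = 8 lines. All 8 end at effective therapy. Four stand under effective-therapy headings and are correct. The other 4 stand under optimal-therapy headings, so 4 of 4 optimal lines carry the wrong event. They repeat the effective-therapy lines word for word.

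| Time zero | Optimal lines with the wrong event | Correct definition elsewhere? |
|---|---|---|
| Lab receipt | 2 (one per set) | Yes: protocol IV.A; SAP Primary outcomes |
| Positivity | 2 (one per set) | No |

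**Time zero of the curves.**

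| Place | Time zeros for optimal and effective therapy |
|---|---|
| Protocol IV.A | Receipt |
| SAP Primary outcomes | Receipt |
| SAP set-specific definitions | Receipt, positivity |
| SAP Figures | Draw, positivity |

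Figures 1A to 1D on the two listed time zeros make 4 × 2 = 8 curve sets: 4 from draw, 4 from positivity, 0 from receipt. For the primary outcome alone (1C and 1D) the count is 2 × 2 = 4, again with 0 from receipt. The SAP lists no panels for Figures 2 to 4, so they are not counted.

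**Can draw be read as receipt?** The SAP's other uses are the test.

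- Total antibiotic days are counted "from date that blood culture was drawn", while the time-to-event lines in the same part of the SAP speak of receipt in the laboratory.
- Time to death runs from when the culture was obtained. The count of deaths within 24 hours of the draw is taken from that same calculation. There, draw means obtained, not received.

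The SAP therefore uses draw and receipt as different points.

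**Effect on results.** This cannot be computed. The documents give no draw-to-receipt interval and no time to effective therapy. The protocol's preliminary data give only that 37% of historical controls reached optimal therapy, at a median of 90 hours among those who did.

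**The case against.** The strongest reply is that nobody would be misled. The headings over the four lines say optimal, as do the titles of Figures 1C and 1D. The Primary outcomes section separates the two events, each set states its own rule for optimal therapy, and the Overview of Analyses lists the two outcomes apart. This stands in large part. A reader might infer that the SAP has replaced the primary event with effective therapy, or that the positivity versions of 1C and 1D would merely repeat 1A and 1B. The documents do not support either inference, since one repeated phrase would have to override all of those places. What remains is that the operative lines for the primary outcome are wrong as written, and that for positivity no other line corrects them.

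On time zero, the definitions list two origins and the figures list two, and positivity is common to both. That parallel makes it plausible that draw was written loosely for receipt. It is a fair reading, but the SAP does not say so and its other uses point the other way. A reader might also infer that the receipt-based analysis has been dropped. It has not: receipt stays in the definitions, and the Overview plans all primary and secondary outcomes. Nor are the draw curves undefined. The figure list gives their time zero and the Primary outcomes section gives the event and censoring. They simply plot a different interval from the defined one.

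A last objection concerns the remedy. Replacing draw throughout the Figures section would also move Figure 1E, in conflict with the SAP's definition of time to death. That objection is right, and it limits the fix.

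**Conclusion.** Both faults hold and should be corrected before the analysis is run. All 4 set-specific lines for optimal therapy name the wrong event; the intended event is recoverable, so this is a correction of wording and not a change of endpoint. None of the 8 curve sets in Figures 1A to 1D starts at lab receipt, so the mismatch covers the effective-therapy panels as well as the primary outcome.

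The second conclusion assumes that draw means collection of the culture, as it does in the SAP's death counts. If it was meant as receipt, the fault shrinks to one word. No claim is made about bias in any estimate, because the size of the effect cannot be derived. Nor is any claim made about the outcome tables, since the rows of Table 3 cannot be read in the available text.

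**What to change.** 1. In the clinician-discretion and pathogen-directed definitions, end the four lines under the optimal-therapy headings at optimal therapy as defined for that set. State that the censoring and contaminant rules of the Primary outcomes section apply.
2. In the Figures section, for the optimal- and effective-therapy curves only (Figures 1A to 1D and any matching panels in Figures 2 to 4), make lab receipt the first time zero. Alternatively, add receipt as the main curve and label draw as supplementary. If draw was meant as receipt, replacing the word for these panels is enough.
3. Leave Figure 1E on the SAP's own origin for time to death, and say so beside the figure list.

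The cost is SAP wording only. Receipt, positivity and first-dose times are already required by the existing definitions, so no new data are needed and neither the design nor patient care changes.

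### In the main comparison, time to pathogen identification is scored by arm label: a late BCID2 in a control is ignored, and a positive BCID2 in the intervention arm counts even if Vitek names another organism

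*SAP*

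**What the plan says.** The rules are in the SAP under Secondary outcomes, Time to pathogen identification. The clock starts at receipt in the laboratory and should stop when a pathogen is identified.

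- **Controls:** "For control patients, this is the time to Vitek". No exception is made for a control who also had a BCID2.
- **Intervention, panel positive:** "If BCID2 positive → calculate time to BCID2 result". Nothing requires Vitek to agree.
- **Intervention, panel negative:** "If BCID2 negative → calculate time to Vitek".

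Three other parts of the SAP bear on this.

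- **Patient Group:** a concurrent control is a patient who "patient was enrolled in the study and did not receive the BCID2 intervention within 12h from blood culture positivity". A later BCID2 does not remove the patient from the group.
- **Protocol deviation:** deviation controls are of two kinds. In one, "BCID2 was sent clinically >12h from positive culture in patient allocated to control group". In the other, the patient was allocated to intervention but no BCID2 was run. Under Overview of Analyses the first comparison is "All interventions vs. all concurrent controls (including protocol deviations) vs. historical controls", for all primary and secondary endpoints.
- **Table 4:** it has rows for "Species misidentification" and for cultures that are positive on BCID2 and negative on Vitek. These are descriptive counts and do not feed into the endpoint.

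**The concern.** The endpoint is meant to record when the organism became known. For two kinds of patient it does not.

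1. A control whose organism was named by a late clinical BCID2 is recorded as unidentified until Vitek reports. The outcomes can then contradict each other. Time to optimal therapy uses the actual dose time, so such a child could reach optimal therapy before the recorded identification.
2. An intervention patient whose BCID2 named the wrong organism, or one that Vitek never found, is recorded as identified at the BCID2 time.

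The first rule can only lengthen control times and the second can only shorten intervention times, so the two cannot offset each other. The endpoint serves secondary aim 2a in the Protocol, the effect of the panel on time to organism identification.

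**Working it through.** **Group sizes (SAP Tables 2 and 2A).** Intervention: 112 per protocol + 23 deviations = 135. Concurrent control: 192 per protocol + 27 deviations = 219. Total: 135 + 219 = 354. All three match the printed figures.

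**Direction.**
- Control with a late positive BCID2: the time to first identification is min(BCID2, Vitek), which is never later than Vitek. Scoring at Vitek lengthens the recorded time or leaves it unchanged.
- Intervention patient with a discordant BCID2: the correct Vitek result comes after the BCID2 result. This relies on BCID2 reporting first. Protocol section C supports it: the panel is run on the flagged bottle, while Vitek waits for colony growth. The documents give no time from positivity to Vitek.

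**Reach of the control rule.** At most 27/219 = 12.3%. The split of the 27 between a late BCID2 and no BCID2 is not given; for those with no BCID2, Vitek is the right time. A per protocol control is defined as having had no BCID2, so none of the 192 is affected. Historical controls were identified by standard culture and Vitek.

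**Size on the control mean.** Shift = (k/219) × gap, where k is the number of controls with a late positive BCID2 and gap is the hours by which it preceded Vitek. Both are assumptions.

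| k | gap 12 h | gap 24 h | gap 30 h | gap 50 h |
|---|---|---|---|---|
| 27 (upper limit) | 1.5 h | 3.0 h | 3.7 h | 6.2 h |
| 13 | 0.7 h | 1.4 h | 1.8 h | 3.0 h |

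For example, 27/219 × 50 = 6.2 and 13/219 × 30 = 1.8.

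The larger gaps need early positivity. With Vitek at the historical median of 78 h, a 50 h gap puts the BCID2 result at 78 − 50 = 28 h. Because it was sent more than 12 h after positivity, the bottle must have flagged before 28 − 12 = 16 h. A 30 h gap needs a flag before 78 − 30 − 12 = 36 h. At the bottom of the historical range (34 h) a 50 h gap is impossible. The documents give no time to positivity.

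**Size on the control median.** Assume Vitek times are normal with mean 78 h and SD 17.6 h. The SD comes from the historical range: 122 − 34 = 88 h, divided by the 5.007 SDs expected as the range of 99 normal values. By simulation, moving all 27 well below the median lowers it by about 3.1 h if they are a random subset and 5.5 h at worst. With 13 the figures are 1.4 h and 2.6 h.

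**Size on the intervention side.** The mean shift is the discordant share times the BCID2-to-Vitek gap. Neither is in the documents, so this is illustration only. Assume BCID2 times are normal with mean 30 h and SD 12 h, and that 10-20% are BCID2-negative. Using the Vitek time for the discordant share then raises the intervention median by:

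- 2% discordant (about 3 of 135): 0.4-0.5 h
- 5% (about 7): 1.0-1.3 h
- 10% (about 14): 2.2-3.0 h

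**The case against.** The best defence is that aim 2a compares the panel with conventional culture, and Vitek is the conventional result. Crediting a control with a clinically sent BCID2 puts the test under study into its own comparator. That is a legitimate question, and a reason to keep the current control rule as a secondary analysis. But the SAP does not give it as the reason, and its main comparison is between groups with deviations included. Nor does it explain why a wrong BCID2 result should count as an identification.

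It is also fair to say that the control side is partly covered. The planned per protocol comparison, for all endpoints, is free of it. That comparison does not help with the intervention side, where discordant positives remain.

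A third objection concerns the remedy. A rule that only Vitek-confirmed results count can fail a BCID2 result but never a Vitek result, so it would tilt the endpoint against the intervention. This stands, and it is why such a rule belongs in a sensitivity analysis.

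A reader might infer that the endpoint never records when the organism was known, or that the reported reduction is certain to be materially overstated. The documents support neither. For at least 192 of 219 controls (87.7%) Vitek is the only identification, and BCID2-negative intervention patients are scored at Vitek. The number of late BCID2 results and the discordance rate are both unknown.

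**Conclusion.** The point holds for the main comparison. Identification time follows the arm label, and both rules can only favour the intervention, given that BCID2 reports before Vitek. The control rule reaches at most 12.3% of concurrent controls. It lengthens their mean by at most 3.7-6.2 h under the assumed 30-50 h gap with all 27 affected, and by about 1.8-3.0 h with 13. The intervention-side effect cannot be sized from the documents. Against a historical median of 78 h the total is probably modest, and nothing shows that it would reverse the finding. It is a one-sided flaw in the definition of a secondary endpoint and should be corrected because the change is cheap.

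**What to change.** 1. **Main comparison.** Score every patient, in every group, at the first positive organism result from either BCID2 or Vitek.
2. **Sensitivity analysis A.** Keep the current rule (controls at Vitek) and label it as the comparison with conventional culture.
3. **Sensitivity analysis B, concordance.** A BCID2 result that disagrees with Vitek on the organism does not stop the clock; use the Vitek time. A resistance-gene mismatch, which Table 4 also lists, is not an organism disagreement and should not trigger this. Keep BCID2-positive, Vitek-negative cultures in the denominator as not identified (censored), and state the censoring time. For polymicrobial cultures use the first concordant organism.
4. **Reporting.** State how many of the 27 deviation controls had a late BCID2.

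Step 1 leaves a discordant positive BCID2 counting as an identification in the main comparison; analysis B shows how much that matters.

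The cost is SAP wording and some data extraction. Classifying deviation controls needs the time at which the BCID2 was sent, but this fix needs the time of its result, so those result times must be retrieved. The reported reduction may be slightly smaller.
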